Assuming a minimum of 4 screws per patient, the estimated probability of at least one non-clinically acceptable screw is 12% in the robotic group and 25% in the navigated and free hand group.

Using a two-sided alpha of 0.05, 80% power, and a 1:6 group ratio, the required sample size is 71 patients in the robotic-assisted surgery group and 426 patients in the non-robotic-assisted surgery group, for a total of 497 patients. We added patients to 75 in the robotic-assisted surgery group, for a total of 501 patients, to be able to include an equal number of patients from Örebro, Umeå and Uppsala. This estimate is conservative, as most patients are expected to receive more than 4 screws, which would increase the likelihood of detecting placement differences.

The primary analysis will use either mixed-effects logistic regression or logistic regression with cluster-robust standard errors to account for intra-patient correlation of screw outcomes.

A secondary analysis of robot-assisted surgeries after the first 501 patients may be performed.

Substudy 2 - Primary outcome - Learning curve (surgical time)

To evaluate the learning curve associated with robotic-assisted surgery, we will model operative time as a function of case number. Operative time is expected to decrease with experience, then plateau. We will use mixed-effects piece-wise linear regression with the surgeon as a random effect to estimate the case number at which operative time levels off. We will look both at wheel-in wheel-out time (primary), and skin-to-skin time (secondary). We expect to do this analysis after each center has performed 100 robot-assisted spine surgeries, in total 300 surgeries.

We have not conducted a traditional power analysis for this substudy, as the objective is not to test a binary hypothesis but to estimate when operative time stabilizes. If no clear inflection point is observed, this will be interpreted as evidence that the learning curve is either very short (already completed), very gradual, or inconsistent. Such a result would itself be informative, and will require us to compare operative times with today's standard of care, navigated or free hand surgery.

Substudy 3- Primary outcome – Reoperation rate at 2 years

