Patient reported outcomes will be collected through the Swedish Spine Register (Swespine) and the Swedish Fracture Register (SFR). Response rates at 1 year is around 75-80%. Response rates in the SFR are lower. The majority of patients will be registered in Swespine (only fracture patients are registered in the SFR). Depending on diagnoses different questionnaires are used. The only questionnaires in Swespine and SFR that are distributed irrespective of diagnoses are EQ-VAS running from 0 (worst) to 100 (best possible health) and EQ-5D. Other questionnaires are Oswestry Disability Index (ODI), Scoliosis Research Society-22revised (SRS-22r), Early Onset Scoliosis Questionnaire-24 (EOSQ-24) and Short Musculoskeletal Function Assessment (SMFA), but are only answered by subpopulations. Several studies indicate that 2 year data does not result in additional information compared to 1 year data, so our primary analysis will use 1 year data, which are available in both Swespine and SFR.

Continuous outcome analysis

EQ-VAS will be analyzed as a continuous variable. We consider a 5-point difference between groups as clinically relevant at the group level, corresponding to a small-to-moderate effect size (Cohen's d appr. 0.25), with an expected standard deviation of 20 points, power 80% and α

0.05. The minimum required number of answering patients in the robotic-assisted group would be 147 and in the non-robotic-assisted group 882. We will exceed this number and achieve a quite reliable estimate if all patients are included in this analysis, also when considering that 30%-40% may not respond to questionnaires in Swespine and SFR.

PASS (Patient Acceptable Symptom State)

We will report the proportion of patients reaching a Patient Acceptable Symptom State (PASS), defined as EQ-VAS ≥ 75 for elective cases and ≥ 65 for non-elective cases. A PASS threshold of 10 percentage point difference in the proportion achieving PASS is considered meaningful. The minimum required number of answering patients in the robotic-assisted group would be 226 and in the non-robotic-assisted group 1,356 if power is 80% and α 0.05. We expect the sample size to provide sufficient power to detect any difference.

15. Recruitment

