Patients will be included consecutively at each site during the enrollment window which is planned to be four years (2025–2029). Currently robotic-assisted spine surgery is available in two hospitals (Umeå and Örebro), with a third hospital waiting for their equipment to be installed (Uppsala). If other hospitals install robotic-assisted surgery during the study period this will just result in more patients involved in the robotic-assisted arm of the trial, which would result in a potentially faster inclusion of the needed amount of patients. We still believe that during the study period more patients will be operated with non-robotic-assisted methods than with robotic-assisted methods.

16–17. Allocation and blinding

No randomization or blinding will be performed. If a planned robotic-assisted surgery is abandoned after the start of surgery, the patient will be included in the robotic-assisted group (i.e. intention to treat principle).

18. Data collection methods

Data will be collected through national registries (Swespine, the Swedish Fracture Register, the Swedish PeriOperative Register, hospital systems (electronic health records, surgical planning software, Picture Archiving and Communication System; PACS and others). PROMs will be recorded preoperatively, and at follow-ups (Swespine: 1, 2 and 5 years; the Swedish Fracture Register: 1 year). Images will be retrieved using standardized CT protocols and assessment will be made by at least two researchers independently.

19. Data management

Data will be collected and managed in compliance with GDPR. Regular validation and updates will occur every 6–12 months. Final datasets will be stored at Uppsala University for a minimum of 15 years.

20. Statistical methods

Statistical analysis will compare outcomes using appropriate parametric or non-parametric tests,

including survival methods. Baseline characteristics will be adjusted for using multivariable models. Adjustment variables include age, diagnosis, comorbidities, previous spine surgery, number of levels, number of screws, robotic system type, use of navigation or free-hand surgery and hospital.

Analysis is currently planned to be performed in R. Interim analyses will be performed when half of the patients have been included. Sensitivity analyses will be performed as described earlier.

21. Data monitoring

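### The adjustment list for the non-randomized 1-year EQ-VAS and PASS comparisons does not name preoperative EQ-VAS, although it is collected

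*Protocol*

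**What the plan says.** Section 14, under patient-reported outcomes, makes 1 year the main time point and says of the score: "EQ-VAS will be analyzed as a continuous variable". The yardstick is a contrast between groups: "We consider a 5-point difference between groups as clinically relevant at the group level". The sizing is made "with an expected standard deviation of 20 points, power 80% and α" 0.05, giving 147 answering robotic patients and 882 others. PASS is a fixed cut of the same score, at 75 for elective and 65 for non-elective cases, with 10 percentage points called meaningful. Neither analysis mentions a change score or a baseline term. EQ-VAS and EQ-5D are the only questionnaires that both registers send regardless of diagnosis.

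Section 18 says "PROMs will be recorded preoperatively, and at follow-ups", and Table 1 in section 12 also shows preoperative collection. Sections 16–17 state that there is no randomization.

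Section 20 commits in general terms to multivariable adjustment for baseline characteristics and then lists variables: "Adjustment variables include age, diagnosis, comorbidities, previous spine surgery, number of levels, number of screws", plus robotic system type, navigation or free-hand use, and hospital. The propensity score list under Substudy 3 in section 14 names no preoperative PROM either.

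**The concern.** A patient's health score before surgery can be expected to relate to the same score a year later. In a non-randomized cohort it may also differ between the groups: the robot is available at two hospitals, with a third awaiting installation, and the protocol itself expects confounding by indication. A preoperative difference that the other covariates do not remove would then be read as an effect of the robot. PASS is exposed in the same way, because it is an absolute threshold on the 1-year score.

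A larger cohort does not help. It narrows the interval around the estimate but leaves the bias where it is. The protocol does not leave covariate choice wholly to a later document. It writes a list, and an analyst who follows that list would leave out the baseline value of the outcome.

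**Working it through.** **1. The plan's own figure.** Inputs from section 14: difference 5, SD 20 (d = 0.25), power 80%, alpha 0.05. Two-sided testing and the 1:6 ratio are stated for Substudy 1 ("Using a two-sided alpha of 0.05, 80% power, and a 1:6 group ratio"). They are not restated for EQ-VAS, but 882/147 = 6.

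n(robotic) = (1 + 1/6) × (1.96 + 0.8416)² / 0.25² = 146.5, rounded up to 147; 6 × 147 = 882.

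The stated figures reproduce exactly, with power 80.1%. They use the full SD of 20, that is, no baseline term.

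**2. Bias if preoperative EQ-VAS is left out.** The carried-over amount is b × D. Here b is the slope of 1-year on preoperative EQ-VAS given group and the listed covariates, and D is the preoperative difference left after those covariates. The documents give neither, so both are assumed.

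| Residual difference D | b = 0.3 | b = 0.6 | Share of the 5-point difference |
|---|---|---|---|
| 2 points | 0.6 | 1.2 | 12–24% |
| 5 points | 1.5 | 3.0 | 30–60% |

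**3. What this means for PASS.** Assume a normal score with SD 20 and a mean near the cut. A shift of s points then moves the proportion by about 0.399 × s/20. For s = 1.5 this is about 3 percentage points and for s = 3.0 about 6, against the 10 called meaningful.

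**4. How far precision is affected.** With baseline/1-year correlation r and equal SDs, adjustment reduces the residual SD to 20 × √(1 − r²).

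| r | Residual SD | Needed, robotic / other |
|---|---|---|
| 0.3 | 19.08 | 134 / 804 |
| 0.5 | 17.32 | 110 / 660 |
| 0.6 | 16.00 | 94 / 564 |

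The study expects far more than 147 robotic responders. Take the smaller Substudy 3 scenario, 420 robotic patients, and the protocol's allowance that "30%-40% may not respond to questionnaires in Swespine and SFR": 420 × 0.7 = 294 and 420 × 0.6 = 252 answer. Unadjusted power for 5 points is then already 97.8% and 95.7%.

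With 252 and 6 × 252 = 1,512 responders, the 95% half-width is 1.96 × 20 × √(1/252 + 1/1,512) = 2.67 points. At r = 0.5 it falls to 2.31. The gain is real but small. By comparison, a carried-over 3.0 points would exceed the unadjusted half-width of 2.67, and a carried-over 0.6 to 1.2 would not.

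**The case against.** The strongest reply is that the protocol does not commit to leaving the score out. Section 20 promises adjustment for baseline characteristics, a preoperative EQ-VAS is one, and the list is introduced as inclusive rather than exhaustive. Section 14 fixes no EQ-VAS model, a SAP may exist, and the section 20 list serves all outcomes, for most of which a PROM would not be expected. The propensity list belongs to the reoperation analysis and says little about EQ-VAS. All of this stands. A reader might infer that the protocol prescribes a comparison unadjusted for baseline, and the documents do not support that. What remains is that the protocol chose to name its covariates and did not name this one. In an unblinded, non-randomized study, leaving it open allows the choice to be made after the data are seen.

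A second reply is that age, diagnosis, comorbidities, previous surgery, levels and hospital may absorb much of any difference in baseline health. That is also right. Only the residual difference counts, and the document contains nothing from which to estimate it. A reader might take 30–60% of the relevant difference as the expected bias. It is only the result of one assumed imbalance.

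A third reply is that the sizing is sound, and it is. A reader might infer that "0.05. The minimum required number of answering patients in the robotic-assisted group would be 147 and in the non-robotic-assisted group 882" is wrong or that the comparison is short of power. The figures reproduce, the protocol presents them as a minimum, and power at the expected numbers is about 96–98%.

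Finally, no preoperative completion rate is given, so it cannot be assumed that every patient, fracture patients in particular, has a usable baseline value.

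**Conclusion.** The point holds as a gap in naming. The section 20 list that governs the 1-year EQ-VAS and PASS comparisons does not name preoperative EQ-VAS, a collected variable that may confound them. If the list is followed as written, a residual preoperative difference of 2 points carries 0.6–1.2 points into the result and one of 5 points carries 1.5–3.0, against a relevant difference of 5. This rests on an assumed conditional slope of 0.3–0.6 and an assumed residual difference.

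It does not show that a bias of this size will occur, nor that the baseline score is the strongest predictor of the outcome, which the documents do not address. The case rests on confounding; the precision gain is secondary. EQ-VAS and PASS are secondary outcomes, so the primary outcomes of the three substudies are untouched.

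**What to change.** Add a sentence to section 20, or to the PROM part of section 14, naming preoperative EQ-VAS as a covariate in the 1-year EQ-VAS model and in the PASS model, alongside the variables already listed. State that missing preoperative values are handled by the multiple imputation of baseline data. That method is now described under Substudy 3 in section 14, so its use for the PROM models should be made explicit. Reporting preoperative completeness by group and register would show how much rests on imputation.

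Letting the baseline slope differ between Swespine and the SFR is optional. The 147 and 882 need no change. The cost is one covariate and a few lines of text. No new data collection is planned for it, since the score is already recorded preoperatively under section 18.
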